7.2.2.10 Visit 13 (Second day of the Month 12 DBPCFC)

Visit 13 corresponds to the second day of the Month 12 DBPCFC. Visit 13 will take place within 7 days after Visit 12. However, Visit 13 may be scheduled up to a maximum of 14 days after Visit 12 and documented in the eCRF, if either of the following occur: (1) the subject experiences reactions after the DBPCFC at Visit 12 that require more than 7 days to elapse before the next food challenge, or (2) any intercurrent disease preventing the second day of the challenge to be conducted safely as planned; in this specific condition, the timeframe between the 2 days of challenges might exceed 14 days and must be appropriately documented, or (3) the subject's schedule or site logistics prevent the second day of food challenge to be performed within 7 days of the first day.

Subjects will undergo the following procedures at this visit:

A physical examination, including a complete skin examination, will be performed before the DBPCFC and can be repeated anytime during the DBPCFC, as judged necessary by the Investigator.

Vital signs (heart rate, systolic and diastolic blood pressure, and respiratory rate) for subjects in a sitting position will be measured before the DBPCFC and can be repeated anytime during the DBPCFC, as judged necessary by the Investigator.

PEF measurements (depending on the subject's age and ability to perform these tests) will be obtained.

DBPCFC will be performed and the grading of each symptom will be made using the grading definitions in the OFC symptom score sheets (see [Appendix 14.2](#)).

Any AEs that have occurred since the previous visit will be documented and any changes in medications reported.

Examination, grading, and photography of the area of the skin used for Viaskin patch application will be performed.

Diary card will be checked and given back to the subject and instructions repeated/reminded, if required.

Site staff will login into IWRS. The treatment kit to be allocated at this Visit 13 should be the first open-label treatment kit for the subject. The Visit 13 treatment box will be dispensed to the subject.

Review/reminder of the utilization of the epinephrine auto-injector and the Anaphylaxis Emergency Action Plan ([Appendix 14.5](#)) as necessary. The expiry date of the auto-injector will be checked and a new auto-injector should be dispensed to the subject, as necessary.

A minimum duration of 3 hours observation after the last dose of the food challenge formula has been ingested is required at this visit, before the subject is discharged from the site. The observation period can be extended beyond 3 hours if deemed necessary by the Investigator.

After completion of the second day of the food challenge ie, after the last dose of the challenge has been administered or the challenge stopped because (a) clear objective reaction(s) has (have) occurred, the order of the challenge formulas can be unblinded and the results of the challenge will be established as described in [Section 7.3.1.1.2](#) and recorded in the eCRF.

Visit 13 corresponds to the start date of the open-label treatment period. If the subject experiences reactions after the DBPCFC at Visit 13 that warrant postponing the application of the first patch of the open-label treatment, it is permitted, at the discretion of the Investigator, to delay the application of the first patch of the open-label treatment up to a maximum of 7 days after Visit 13.

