A physical examination, including a complete skin examination, will be performed before the DBPCFC and can be repeated anytime during the DBPCFC, as judged necessary by the Investigator.

Vital signs (heart rate, systolic and diastolic blood pressure, and respiratory rate) for subjects in a sitting position will be measured before the DBPCFC and can be repeated anytime during the DBPCFC, as judged necessary by the Investigator.

PEF measurements (depending on the subject's age and ability to perform these tests) will be obtained.

Any AEs that have occurred since the previous visit will be documented and any changes in medications reported.

DBPCFC will be performed and the grading of each symptom will be made using the grading definitions in the OFC symptom score sheets ([see Appendix 14.2](#)).

A minimum duration of 3 hours observation after the last dose of the food challenge formula has been ingested is required at this visit, before the subject is discharged from the site. The observation period can be extended beyond 3 hours if deemed necessary by the Investigator.

After completion of the second day of the food challenge, ie, after the last dose of the challenge has been administered or the challenge stopped because of (a) clear

objective reaction(s) has (have) occurred, the order of the challenge formulas can be unblinded and the results of the challenge will be established as described in [Section 7.3.1.1.1](#) and recorded in the eCRF.

This will be the last criterion to determine whether the subject is eligible to be randomized to treatment or not. If the subject is not eligible for participation in the study, the site staff must go into IWRS to register the subject as Screen Failure. If the subject is eligible for participation in the study, the site staff must go into IWRS to register the subject for randomization once the Cohort or Part is open for randomization. Randomization by IWRS can be performed as soon as the eligibility of the subject is confirmed at the end of Visit 3, and up to the day of Visit 4.

7.2.2 *Part A, Part B, 12-month open-label treatment with Viaskin Milk 500 µg and study extension*

The following visit schedule applies until Protocol Amendment 5 is approved and the subjects switch to Viaskin Milk 300 µg. However, no further DBPCFC should be conducted while the subjects are still receiving Viaskin Milk 500 µg.

Refer to [Section 7.2.3](#) as soon as the Viaskin Milk 300 µg is available at the study site.

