A DBPCFC will be performed at screening (Visits 2 and 3), at Month 12 (Visits 12 and 13); a DBPCFC was planned at Month 24 (Visits 16 and 17) and for subjects who entered the study extension, at Month 36 (Visits 19 and 20) and Month 48 (Visits 22 and 23), but these food challenges should no longer be performed while the subjects are still receiving Viaskin Milk 500 μ g. A DBPCFC can be performed after 12 months (Visits S3 and S4) and/or 24 months (Visits S6 and S7) of treatment with Viaskin Milk 300 μ g, at the decision of the Investigator and the subject.

No DBPCFC will be performed while the subjects are still receiving Viaskin Milk 500 μ g and until they reach 12 months of treatment with Viaskin Milk 300 μ g.

Each DBPCFC will comprise 2 visits: 1 visit for the Placebo Challenge and 1 visit for the Milk Challenge. The order of the 2 formulas is not known to the medical team until the end of the second day of the challenge. The second day of the food challenge should take place within 7 days (one week) after the first day of the food challenge. However, the second day may be scheduled up to a maximum of 14 days after the first food challenge and documented in the eCRF, if any of the following occurs: (1) the subject experiences reactions after the DBPCFC on the first day that require more than 7 days to elapse before the next food challenge, or (2) any intercurrent disease preventing the second day of the challenge to be conducted safely as planned, such as a rhinitis, bronchitis or gastrointestinal infection; in this specific condition and for safety reasons, the timeframe between the 2 days of challenges might exceed 14 days and must be appropriately documented, or (3) the subject's schedule or site logistics prevent the second day of food challenge to be performed within 7 days of the first day.

The order of the food challenge (milk or placebo) will be blinded; it will be determined using a randomization table that will be distributed to site personnel dedicated to the preparation of the challenge formulas (see [Section 8.4](#)). After both days of a DBPCFC have been completed, the order of the food challenge (ie, actual visits that the milk and placebo challenges were administered) can be revealed for completion of the eCRF.

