At the end of the second day of the food challenge (Visit 3), the sequence of the 2 formulas (milk or placebo) administered to the subject will be unblinded by the appropriate unblinded staff (eg, dieticians, study nurses, pharmacists, pharmacy technicians, licensed medical assistants, or any other qualified site personnel, as delegated by the Investigator) and revealed to the medical staff. The results of the challenge will then be established and recorded in the eCRF as follows:

1. The subject had objective symptoms to the placebo formula at any dose leading to stopping the challenge. S/He cannot be randomized in the study.
2. The subject had no objective symptoms during the 2 days of the DBPCFC, neither to the placebo nor to the milk formula, even at the highest dose of 300 mg of cow's milk proteins. S/He is considered not allergic enough to cow's milk to participate in this study and cannot be randomized in the study.
3. The subject had no objective symptom when receiving placebo but had an objective reaction (as defined in [Section 7.3.1.1.3](#)) at 1 of the doses of the milk formula consumed between 1 mg and 300 mg inclusive. S/He will be randomized in the study as s/he reacted to a dose of milk proteins lower than or equal to 300 mg (eliciting dose).

7.3.1.1.2 DBPCFC at Month 12 (Visits 12 and 13), Month 24 (Visits 16 and 17), Month 36 (Visits 19 and 20), and Month 48 (Visits 22 and 23), and optional DBPCFC after 12 months (Visits S3 and S4) and 24 months (Visits S6 and S7) of treatment with Viaskin Milk 300 µg

No patch should be applied on the day of the DBPCFC until all DBPCFC procedures have been completed.

Following results of the 12-month blinded period, the DBPCFCs that were to be performed at Month 24, Month 36 and Month 48 should not be conducted while the subjects are still receiving Viaskin Milk 500 µg.

After subjects switch to Viaskin Milk 300 µg, the DBPCFCs at 12 months and 24 months will be optional and left at the Investigator's and the subject's decision. However, if a subject experienced a severe anaphylaxis to cow's milk during the MILES study, whether or not occurring during the DBPCFC, no further DBPCFC should be conducted for this subject.

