All DBPCFCs at Month 12 and forward will be conducted using the same procedures that are described for the screening DBPCFC, with the exception that the dosing will continue beyond the 300 mg dose of cow's milk proteins if there are no objective symptoms (see [Section 7.3.1.1.3](#)) at the 300 mg dose. The challenge must be continued up to the last dose of 3000 mg of cow's milk proteins or until an objective reaction occurs (as defined in [Section 7.3.1.1.3](#)).

For all DBPCFCs at Month 12 and forward, the doses of cow's milk proteins will be 1 mg, 3 mg, 10 mg, 30 mg, 100 mg, 300 mg, 1000 mg, 2000 mg, and 3000 mg administered at 20-minute intervals. The Investigator may use clinical judgment to increase the intervals between doses in case there is a suspicion that an objective reaction may be developing (see [Section 7.3.1.1.3](#)). Very occasionally, the Investigator may use clinical judgment to repeat the same dose (only once) before administration of the next higher dose and only if there is a suspicion that an objective reaction may be developing (see [Section 7.3.1.1.3](#)). The dose and time of administration of each dose (and of a repeated dose when applicable) will be recorded in the eCRF. The subjects

will be kept under observation for an additional 3 hours after the ingestion of the last dose of the challenge formula.

Subjects should undergo both days of the DBPCFC (milk and placebo). However, in exceptional cases, the DBPCFC on the second day of the challenge might not be performed if the subject had a severe anaphylactic reaction during the first day of the challenge, leaving no doubt about the nature of the formula administered, ie, cow's milk. In this rare case and in this case only, the formula will be unblinded to confirm that the subject effectively received the milk formula. A severe anaphylactic reaction would involve a >20% drop of blood pressure, cyanosis or SpO₂<92%, confusion, collapse, loss of consciousness, 3 doses of epinephrine or more (see [Appendix 14.4](#)).

At the end of the second day of the food challenge, the sequence of the 2 formulas (milk or placebo) administered will be unblinded by the appropriate unblinded staff (eg, dieticians, study nurses, pharmacists, pharmacy technicians, licensed medical assistants, or any other qualified site personnel, as delegated by the Investigator) and revealed to the medical staff. The results of the challenge will then be established and recorded in the eCRF.

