subject information and the table will populate automatically to determine which formula (Milk or placebo) is given on the first day of the food challenge and which formula (Milk or placebo) will be given the second day of the challenge. The subject and the assessors will remain blind to the formulas' order during the conduct of the challenge on both days (see [Section 7.3.1.1](#) for emergency unblinding procedures). Only at the end of the second day of challenge will the order of the formulas be unblinded to the subject and the assessors.

9 Quality Assurance and Quality Control

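### The milk/placebo order may be revealed right after the last dose on challenge day 2, before the 3-hour observation ends, so late reactions on that day can be judged with the formula known

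*Protocol*

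**What the plan says.** The visit-level text of the protocol sets an early point for the reveal.

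- **Visit 13 (7.2.2.10):** "After completion of the second day of the food challenge ie, after the last dose of the challenge has been administered", or once a clear objective reaction has stopped the challenge, "the order of the challenge formulas can be unblinded and the results of the challenge will be established as described in" Section 7.3.1.1.2.
- **Visit 3 (7.2.1.3), screening:** "After completion of the second day of the food challenge, ie, after the last dose of the challenge has been administered". The rest of the sentence matches Visit 13.
- **Visits 17, 20, 23, S4 and S7:** the same sentence again.

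Visit 13 also requires observation, counted from the same dose: "A minimum duration of 3 hours observation after the last dose of the food challenge formula has been ingested is required at this visit".

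The general sections use a different expression. Section 8.4 says: "Only at the end of the second day of challenge will the order of the formulas be unblinded to the subject and the assessors". Section 7.3.1.1 keeps the medical team unaware until the second day has ended, then says the order "can be revealed for completion of the eCRF" once both days have been completed. SAP 3.4.3 follows 8.4. Sections 7.3.1.1.1 and 7.3.1.1.2 place the reveal first and continue: "The results of the challenge will then be established and recorded in the eCRF".

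**The concern.** The challenge is double-blind so that an ambiguous sign is judged in the same way on the milk day and the placebo day. Some signs do need judgement: Section 7.3.1.1.3 (in its rules for the 300 µg open-label challenges) asks the investigator to separate laryngeal oedema from transient irritation, and allergic vomiting from spitting up. If the formula is known during the observation, that protection is lost for the part of day 2 in which reactions to the last dose would appear.

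Four things are exposed:

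- eligibility of a child who has no clear reaction when the 300 mg screening dose is given on day 2 and qualifies only if an objective reaction is called afterwards;
- the severity scores, which sum symptom grades (SAP 8.2.5.1), with the worst grade per symptom and visit used in the 300 µg open-label period (SAP 8.2.5.2);
- time to first objective symptom, which is censored at discharge and so takes in the observation period (Protocol 8.1.6.2.5, SAP 8.2.5.1);
- the tables that compare reactions by milk and placebo formula (SAP 8.2.5.1, 9.4), where a late placebo-day sign may be discounted.

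**Working it through.** The plan states no figure for the timing of the reveal, so the main check sets the passages side by side. Arithmetic then shows what is and is not exposed.

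**1. Order of events on day 2.** Take the last dose as time zero.

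- Earliest permitted reveal: time zero, or the moment the challenge is stopped (7.2.1.3, 7.2.2.10 and the later visits).
- Observation: from the last dose to at least 180 minutes (same visits).
- Results established and recorded: after the reveal (7.3.1.1.1, 7.3.1.1.2).
- Symptom grades final before the reveal: required nowhere. Section 7.3.1.1.3 asks for symptom times and grades in the eCRF but does not tie this to the reveal.

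The end of the second day, as used in 7.3.1.1 and 8.4, could mean after observation. Neither section says so, and the only definition given is the earlier one in the visit text.

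**2. Time exposed.** Doses are 20 minutes apart.

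- Screening, six doses: 5 × 20 = 100 minutes of dosing; 180 / (100 + 180) = 64% of the minimum day-2 time follows the permitted reveal.
- Month 12, all nine doses: 8 × 20 = 160 minutes; 180 / (160 + 180) = 53%.

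These are shares of clock time on a nominal schedule, not of reactions or decisions. Day 1 is observed blind throughout.

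**3. Month 12 responder status.** Protocol 8.1.6.1 defines the cumulative reactive dose (CRD) as the sum of all doses given. For 1, 3, 10, 30, 100, 300, 1000, 2000 and 3000 mg without repeats, the running totals are 1, 4, 14, 44, 144, 444, 1444, 3444 and 6444 mg. This reproduces the plan's two thresholds: 144 mg after the 100 mg dose and 1444 mg after the 1000 mg dose.

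- A child stopped at any step was stopped before the permitted reveal, and the total is already fixed.
- A child who takes all nine doses has 6444 mg, which is at least 1444 mg, and is a responder whatever is seen afterwards.

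**4. Screening.** The screening challenge ends at 300 mg whether or not a reaction has occurred, and observation follows (7.3.1.1.1). The total at that point is 1 + 3 + 10 + 30 + 100 + 300 = 444 mg, so the baseline value is fixed too. What remains open is whether an objective reaction occurred at all, and that decides entry.

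**5. Placebo formula at screening.** Exclusion criterion 7 needs objective symptoms that led to stopping. A stop comes before the permitted reveal, so it is called blind. Only a late placebo sign that stopped nothing is exposed.

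**The case against.** The strongest reply has five parts.

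- **The text permits the reveal but does not order it.** A Manual of Procedures, not among the documents, may set a later time. This stands as a limit on what can be said about conduct, but the protocol should not permit what a manual would have to forbid.
- **The primary endpoint is not at risk.** This stands. A reader might infer that Month 12 responder status is judged unblinded; steps 3 and 4 of the working show that the doses given settle both the Month 12 and the baseline totals.
- **There is no route to bias between arms.** A reader might infer that the reveal unmasks treatment. It does not: Protocol 6.4 keeps patch allocation blinded until all 12-month data are collected, and the challenge order says nothing about the arm. For severity and time to first objective symptom at Month 12, SAP 8.2.5.1 gives summaries and Kaplan-Meier curves without a between-arm test.
- **Milk results cannot be labelled as milk without the order.** True, but grades and times can be made final as Day 1 and Day 2 before the label is added.
- **Most of these challenges are over.** This also stands. The Month 12 analysis has been done (Protocol 3.1, SAP 3.1), and Visits 17, 20 and 23 no longer apply (notes to Protocol Tables 2 to 5). Only the optional, open-label S4 and S7 challenges can still be governed by new wording.

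**Conclusion.** The point holds as a gap in the challenge blind. The visit text allows the reveal before observation ends, the general sections do not clearly overrule it, and nothing requires the day's symptom findings to be final first. The exposure is confined to the observation part of day 2 and to the four items listed under the concern.

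Its size cannot be derived. The documents do not give the frequency of late reactions, the share that are ambiguous, or how often sites revealed the order at once. A reader might infer that less reactive children were admitted, raising response in every arm and costing power. That needs an assumed rate of wrong entry for which the documents offer no basis, and the sample-size text is redacted, so no power figure is given here.

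The conclusion assumes that the visit text was applied as written and that no manual sets a later time. It is a free improvement, not a threat to the Month 12 responder result.

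**What to change.** Replace the explanatory clause in the visit text. The order may be revealed only when the day-2 observation has ended and the symptom score sheets, stopping reason and doses for both days have been completed and signed, labelled Day 1 and Day 2. The formula order is then added to the eCRF. Emergency unblinding stays unchanged. Align Sections 7.3.1.1, 7.3.1.1.1, 7.3.1.1.2 and 8.4, the matching sentence in SAP 3.4.3, and the Manual of Procedures if it differs.

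Apply this to S4 and S7. For the completed screening and Month 12 challenges, check where records allow whether the order was revealed before observation ended, and state the finding in the report beside the severity, time-to-symptom and formula-specific tables.

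The cost is wording plus a look at existing records. No procedure or staff are added, and the reveal comes about 3 hours later.

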7.2.2.11 Visit 14 (21 days ±3 days after Visit 13)

Visit 14 will take place 21 days ±3 days after Visit 13.

Subjects will undergo the following procedures at this visit:

A physical examination, including a complete skin examination, will be performed.

Vital signs (heart rate, systolic and diastolic blood pressure, and respiratory rate) for subjects in a sitting position will be measured.

PEF measurements (depending on the subject's age and ability to perform these tests) will be obtained.

Any AEs that have occurred since the previous visit will be documented and any changes in medications reported.

Examination, grading, and photography of the area of the skin used for Viaskin patch application will be performed.

Diary card will be checked and given back to the subject and instructions repeated/reminded, if required.

The Visit 13 treatment box will be collected from the subject and drug accountability/compliance will be assessed.

The Visit 14 treatment box will be dispensed to the subject.

Review/reminder of the utilization of the epinephrine auto-injector and the Anaphylaxis Emergency Action Plan ([Appendix 14.5](#)) as necessary. The expiry date of the auto-injector will be checked and a new auto-injector should be dispensed to the subject, as necessary.

7.2.2.12 Visit 15 (Month 18 ±14 days)

Visit 15 (Month 18) will take place 6 months ±14 days after Visit 13.

Subjects will undergo the following procedures at this visit:

Weight (kg) and height (cm) will be measured.

A physical examination, including a complete skin examination, will be performed.

Vital signs (heart rate, systolic and diastolic blood pressure, and respiratory rate) for subjects in a sitting position will be measured.

Spirometry and PEF measurements (depending on the subject's age and ability to perform these tests) will be obtained.

SPT to cow's milk will be performed.

Blood samples for hematology and biochemistry laboratory tests, as well as immunological markers (IgE, IgG4) will be collected.

Only for subjects who signed the genetic ICF/IAF: a blood sample for the analysis of filaggrin mutations may be collected at this visit if not collected at a previous visit.

Any AEs that have occurred since the previous visit will be documented and any changes in medications reported.

Examination, grading, and photography of the area of the skin used for Viaskin patch application will be performed.

Diary card will be checked and given back to the subject and instructions repeated/reminded, if required.

The Visit 14 treatment box will be collected from the subject and drug accountability/compliance will be assessed.

Site staff will login into IWRS to be allocated a re-supply open-label kit for the subject. The Visit 15 treatment box will be dispensed to the subject.

Review/reminder of the utilization of the epinephrine auto-injector and the Anaphylaxis Emergency Action Plan ([Appendix 14.5](#)) as necessary. The expiry date of the auto-injector will be checked and a new auto-injector should be dispensed to the subject, as necessary.

7.2.2.13 Visit 16 (Month 24 ±14 days; First Day of the Month 24 DBPCFC)

Before implementation of Protocol Amendment 5

Visit 16 (Month 24) will take place 12 months ±14 days after Visit 13. Visit 16 corresponds to the first day of the Month 24 DBPCFC. It is recommended that a patch not be applied on that day until all DBPCFC procedures have been completed.

Subjects will undergo the following procedures at this visit:

QoL questionnaire FAQLQ/FAIM forms ([Appendix 14.3](#)) will be completed by subjects (when applicable) and parent(s)/guardian(s) before any procedures at this visit are performed. The appropriate QoL questionnaire forms to complete depend upon the age of the subject at the time of Visit 1.

Weight (kg) and height (cm) will be measured.

A physical examination, including a complete skin examination, will be performed before the DBPCFC and can be repeated anytime during the DBPCFC, as judged necessary by the Investigator.

Vital signs (heart rate, systolic and diastolic blood pressure, and respiratory rate) for subjects in a sitting position will be measured before the DBPCFC and can be repeated anytime during the DBPCFC, as judged necessary by the Investigator.

Spirometry and PEF measurements (depending on the subject's age and ability to perform these tests) will be obtained.

SPT to cow's milk will be performed.

Blood samples for hematology and biochemistry laboratory tests, and immunological markers (IgE, IgG4) will be collected.

Only for subjects who signed the genetic ICF/IAF: a blood sample for the analysis of filaggrin mutations may be collected at this visit if not collected at a previous visit.

Only for subjects who signed the genetic ICF/IAF: a blood sample for epigenetic analysis will be collected.

A urine pregnancy test will be performed for female subjects with childbearing potential.

DBPCFC will be performed and the grading of each symptom will be made using the grading definitions in the OFC symptom score sheets (see [Appendix 14.2](#)).

Any AEs that have occurred since the previous visit will be documented and any changes in medications reported.

Examination, grading, and photography of the area of the skin used for Viaskin patch application will be performed.

Diary card will be checked and given back to the subject and instructions repeated/reminded, if required.

The Visit 15 treatment box will be collected from the subject and drug accountability/compliance will be assessed.

Site staff will login into IWRS to be allocated a small re-supply open-label kit to cover the period between both days of the DBPCFC. The Visit 16 treatment box will be dispensed to the subject.

Review/reminder of the utilization of the epinephrine auto-injector and the Anaphylaxis Emergency Action Plan ([Appendix 14.5](#)), as necessary. The expiry date of the auto-injector will be checked and a new auto-injector should be dispensed to the subject, as necessary.

A minimum duration of 3 hours observation after the last dose of the food challenge formula has been ingested is required at this visit, before the subject is discharged from the site. The observation period can be extended beyond 3 hours if deemed necessary by the Investigator.

After implementation of Protocol Amendment 5

Until the subjects can switch to Viaskin Milk 300 µg, the following will apply:

- The Visit 16 will proceed without the procedures related to the DBPCFC;
- Site staff will login into IWRS to be allocated treatment kits for both Visit 16 and Visit 17;
- Visit 17 will not be conducted.

7.2.2.14 *Visit 17 (Second day of the Month 24 DBPCFC) - Not to be conducted after implementation of Protocol Amendment 5*

Visit 17 corresponds to the second day of the Month 24 DBPCFC. It is recommended that a patch not be applied on that day until all DBPCFC procedures have been completed.

Visit 17 will take place within 7 days after Visit 16. However, Visit 17 may be scheduled up to a maximum of 14 days after Visit 16 and documented in the eCRF, if either of the following occur: (1) the subject experiences reactions after the DBPCFC at Visit 16 that require more than 7 days to elapse before the next food challenge, or (2) any intercurrent disease preventing the second day of the challenge to be conducted safely as planned; in this specific condition, the timeframe between the 2 days of challenges might exceed 14 days and must be appropriately documented, or (3) the subject's schedule or site logistics prevent the second day of food challenge to be performed within 7 days of the first day.

Subjects will undergo the following procedures at this visit:

A physical examination, including a complete skin examination, will be performed before the DBPCFC and can be repeated anytime during the DBPCFC, as judged necessary by the Investigator.

Vital signs (heart rate, systolic and diastolic blood pressure, and respiratory rate) for subjects in a sitting position will be measured before the DBPCFC and can be repeated anytime during the DBPCFC, as judged necessary by the Investigator.

PEF measurements (depending on the subject's age and ability to perform these tests) will be obtained.

DBPCFC will be performed and the grading of each symptom will be made using the grading definitions in the OFC symptom score sheets (see [Appendix 14.2](#)).

Any AEs that have occurred since the previous visit will be documented and any changes in medications reported.

Examination, grading, and photography of the area of the skin used for Viaskin patch application will be performed.

Diary card will be checked and given back to the subject and instructions repeated/reminded, if required.

The Visit 16 treatment box will be collected from the subject and drug accountability/compliance will be assessed.

Review/reminder of the utilization of the epinephrine auto-injector and the Anaphylaxis Emergency Action Plan ([Appendix 14.5](#)), as necessary. The expiry date of the auto-injector will be checked and a new auto-injector should be dispensed to the subject, as necessary.

A minimum duration of 3 hours observation after the last dose of the food challenge formula has been ingested is required at this visit, before the subject is discharged from the site. The observation period can be extended beyond 3 hours if deemed necessary by the Investigator.

After completion of the second day of the food challenge ie, after the last dose of the challenge has been administered or the challenge stopped because of (a) clear objective reaction(s) has (have) occurred, the order of the challenge formulas can be unblinded and the results of the challenge will be established as described in [Section 7.3.1.1.2](#) and recorded in the eCRF.

After the second day of the Month 24 DBPCFC, eligible subjects will be proposed to enter the study extension to receive 2 additional years of EPIT with open-label Viaskin Milk 500 µg. Subjects who enter the study extension will undergo the following additional procedures:

Written and signed ICF/IAF to enter study extension will be collected at Visit 17, if not collected previously.

Eligibility criteria to enter study extension will be assessed.

Site staff will login into IWRS to be allocated a re-supply open-label kit for the subject. The Visit 17 treatment box will be dispensed to the subject.

For the subjects who do not enter the study extension, there will be no dispensation of the Investigational Product at this visit. It will be the end of the open-label treatment period. A final EOS follow-up visit will take place 14 days after Visit 17.

